2.1 Purpose of the Analyses

This Phase I/II trial will serve to assess whether ETVAX is safe and provides mucosal as well as systemic immune responses against the key protective antigens when tested in different age-groups in Bangladesh. This study provides an opportunity to test the safety profile of a mucosal adjuvant, double-mutant LT (dmLT), in adults and children, as well as provides the opportunity to potentially assess the ability of dmLT to further enhance the mucosal and systemic antibody responses to key antigens in the ETVAX vaccine among age groups in developing country sites, like Bangladesh, that have proved refractory to oral immunization with enteric vaccines. In addition, this study also allows for the evaluation of the potential dose-sparing effect of dmLT when combined with a lower dose of vaccine. Finally, this clinical trial is considered an essential study along the critical path of the overall clinical development plan before determining whether the vaccine can be tested for protective efficacy in children in developing countries.

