3 STUDY OBJECTIVES AND ENDPOINTS

3.1 Study Objectives

3.1.1 Primary Objective

The primary objective deals with safety and tolerability and is the following:

• To evaluate the safety and tolerability of orally administered ETVAX, containing 4 different inactivated *E. coli* strains over-expressing CFA/I, CS3, CS5 and CS6 and a hybrid LCTBA protein, given along and together with different dosages of dmLT adjuvant in descending age groups in Bangladesh.

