9.1.1 Solicited Events and Symptoms

Solicited adverse events will be collected pre-vaccination, 60 minutes post-vaccination and then daily for 7 days after vaccination and graded on a scale of 0 (absent), 1 (mild), 2 (moderate) and 3 (severe). Solicited events include: elevated oral temperature, nausea, vomiting, loose stools, diarrhea, abdominal pain/stomach ache, and acute systemic allergic reaction. Adults will have all events collected. Toddlers (24 - 59 months) will have all events except nausea collected and Younger Children (12 - 23 Months) and Infants (6 - 11 months) will only have oral temperature, vomiting, loose stools, diarrhea and acute systemic allergic reaction collected.

The proportion of participants reporting at least one solicited adverse event within 7 days of any vaccination will be summarized for each solicited adverse event and for any solicited adverse event. The 95% CI calculated using Clopper-Pearson methodology from a binomial distribution (SAS Proc Freq with a binomial option) will be presented (Tables 14.3.1.1(a)(b)(c)(d)).

For each solicited adverse event and for any solicited adverse event, the maximum severity over 7 days after each vaccination will be summarized for the Safety population. The number and percentage of participants reporting each event will be summarized for each treatment group by the maximum severity. For each event the denominator is the number of participants with non-missing data for the specific event (Tables 14.3.1.2(a)(b)(c)(d)).

The number and percentage of participants reporting any solicited adverse event and reporting each individual solicited adverse event will be summarized for each day post vaccination for each vaccination by Treatment group (Tables 14.3.1.3(a)(b)(c)(d)) and severity. The percent of participants reporting any solicited event will be displayed graphically in a bar chart in Figures 14.3.1.4(a)(b)(c)(d)).

Fisher's exact test will be used to compare the proportion of participants with solicited reactogenicity events between each of the vaccine arms with the placebo arms. In addition, the vaccine arms without dmLT will be combined, the vaccine arms with dmLT will be combined and all vaccine arms will be combined and each will be compared to placebo. The results will be summarized in Tables 14.3.1.5(a)(b)(c)(d).

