A logistic regression analysis will be presented to look at the proportion of vomiting after any ETVAX dose, with covariates for sex, age group (i.e., cohort's B, C and D), dose and adjuvant in the model. The age group categories will correspond with cohorts B, C and D: 6-11 months, 12-23 months, and 24-59 months, respectively. Results will be summarized for all vaccinated children in Table 14.3.1.6.1 and all children in Table 14.3.1.6.2.

The primary purpose of the statistical comparisons is to screen out potential solicited reactogenicity events that need further clinical evaluation. Therefore, they are not considered formal statistical hypothesis tests and it is acknowledged that there will be inflated Type I errors (i.e., inflated false statistical significances) from performing multiple unadjusted comparisons.

Solicited adverse events by participant will be presented in Listings 16.2.7.1(a)(b)(c)(d).

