Symptom	n	%	n	%	P-value ^a	n	%	P-value ^a
Any Symptom	XX	XX.X	xx	XX.X	0.xxx	XX	XX.X	0.xxx
Elevated Oral Temperature	xx	XX.X	XX	XX.X	0.xxx	xx	xx.x	0.xxx
Nausea	XX	XX.X	xx	XX.X	0.xxx	XX	XX.X	0.xxx
Vomiting	XX	XX.X	xx	XX.X	0.xxx	XX	XX.X	0.xxx
Loose stools	xx	XX.X	XX	XX.X	0.xxx	xx	xx.x	0.xxx
Diarrhea	XX	xx.x	XX	XX.X	0.xxx	XX	XX.X	0.xxx
Abdominal pain/stomach ache	xx	XX.X	XX	XX.X	0.xxx	XX	xx.x	0.xxx
Acute systemic allergic reaction	XX	xx.x	XX	XX.X	0.xxx	XX	XX.X	0.xxx

N = Number of participants in the Safety population; n = Number of participants with a symptom reported post-vaccination.

^a P-value is from a Fisher's exact test, testing the treatment vs placebo.

TABLE 14.3.1.5b: Comparison of the Proportion of Participants Experiencing Solicited Events by Treatment Group - Toddlers (24 - 59 Months)

		ecebo =XX)	E	TVAX 1 (N=X	/4 Dose XX)	E	TVAX 1/ (N=X		ET	VAX F (N=X	'ull Dose XX)		mbined l	ETVAX =XX)
Symptom	n	%	n	%	P-value ^a	n	%	P-value ^a	n	%	P-value ^a	n	%	P-value ^a
Any Symptom	XX	XX.X	XX	xx.x	0.xxx	XX	XX.X	0.xxx	XX	xx.x	0.xxx	XX	XX.X	0.xxx
Elevated Oral Temperature	XX	XX.X	XX	xx.x	0.xxx	XX	XX.X	0.xxx	XX	xx.x	0.xxx	XX	XX.X	0.xxx
Vomiting	XX	XX.X	XX	xx.x	0.xxx	XX	XX.X	0.xxx	XX	XX.X	0.xxx	XX	XX.X	0.xxx
Loose stools	XX	XX.X	XX	xx.x	0.xxx	XX	XX.X	0.xxx	XX	XX.X	0.xxx	XX	XX.X	0.xxx
Diarrhea	XX	XX.X	XX	XX.X	0.xxx	XX	XX.X	0.xxx	XX	XX.X	0.xxx	XX	XX.X	0.xxx
Abdominal pain/stomach ache	XX	XX.X	XX	xx.x	0.xxx	XX	XX.X	0.xxx	XX	XX.X	0.xxx	XX	XX.X	0.xxx
Acute systemic allergic reaction	XX	XX.X	XX	XX.X	0.xxx	XX	XX.X	0.xxx	XX	XX.X	0.xxx	XX	XX.X	0.xxx

	` `	ETV. shest sat 2.5 µg d (N=)	fe dose) + lmLT	(hig	ETVA shest safe 5 µg dn (N=X	e dose) + nLT	` 0	ETV hest sat 10 µg d (N=)	fe dose) + lmLT	Co	ombined l + dml (N=X)	LT
Symptom	n	%	P-value ^a	n	%	P-value ^a	n	%	P-value ^a	n	%	P-value ^a
Any Symptom	XX	XX.X	0.xxx	XX	XX.X	0.xxx	XX	XX.X	0.xxx	XX	XX.X	0.xxx
Elevated Oral Temperature	XX	XX.X	0.xxx	XX	XX.X	0.xxx	XX	XX.X	0.xxx	XX	XX.X	0.xxx
Vomiting	XX	XX.X	0.xxx	XX	XX.X	0.xxx	XX	XX.X	0.xxx	XX	XX.X	0.xxx
Loose stools	XX	XX.X	0.xxx	XX	XX.X	0.xxx	XX	XX.X	0.xxx	XX	XX.X	0.xxx
Diarrhea	XX	XX.X	0.xxx	XX	XX.X	0.xxx	XX	xx.x	0.xxx	XX	xx.x	0.xxx
Abdominal pain/stomach ache	XX	xx.x	0.xxx	XX	XX.X	0.xxx	XX	xx.x	0.xxx	XX	XX.X	0.xxx
Acute systemic allergic reaction	xx	xx.x	0.xxx	XX	XX.X	0.xxx	XX	xx.x	0.xxx	XX	XX.X	0.xxx

N = Number of participants in the Safety population; n = Number of participants with a symptom reported post-vaccination.

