Elevated Oral Temperature	XX	XX.X	0.xxx	XX	XX.X	0.xxx	XX	XX.X	0.xxx	XX	XX.X	0.xxx
Vomiting	XX	XX.X	0.xxx	XX	XX.X	0.xxx	XX	XX.X	0.xxx	XX	XX.X	0.xxx
Loose stools	XX	XX.X	0.xxx	XX	XX.X	0.xxx	XX	XX.X	0.xxx	XX	XX.X	0.xxx
Diarrhea	XX	XX.X	0.xxx	XX	XX.X	0.xxx	XX	XX.X	0.xxx	XX	XX.X	0.xxx
Acute systemic allergic reaction	XX	XX.X	0.xxx	XX	XX.X	0.xxx	XX	xx.x	0.xxx	XX	XX.X	0.xxx

N = Number of participants in the Safety population; n = Number of participants with a symptom reported post-vaccination.

^a P-value is from a Fisher's exact test, testing the treatment vs placebo.

TABLE 14.3.1.6.1: Univariate and Adjusted Odds of Vomiting after any ETVAX Dose (Day 0) Among Vaccinated Children 6 to 59 Months of Age

			Logistic Reg	gression: OR (95% CI)
Variable	Vomiteda	No vomiting	Univariate	Adjusted
Sex				
Female	n (%) ^b	n	OR (95% CI)	OR (95% CI)
Male	n (%)	n	1	1
Age (months)				
6 to 11				
12 to 23				
24 to 59			1	1
dmLT (mcg)				
0				
2.5				
5.0				
10.0			1	1
Dose ^c				
1/8				
1/4				
1/2			1	1

^aMild or greater vomiting after first, second, or both doses on day 0.

^bn (percent of row total)

^cExclude full dose recipients (n=5) from analysis.

TABLE 14.3.1.6.2: Univariate and Adjusted Odds of Vomiting after any ETVAX Dose (Day 0) Among All Children 6 to 59 Months of Age

			Logistic	Regression
Variable	Vomited ^a	No vomiting	Univariate	Adjusted
Sex				
Female	n (%) ^b	n	OR (95% CI)	OR (95% CI)
Male	n (%)	n	1	1
Age (months)				
6 to 11				
12 to 23				
24 to 59			1	1
Dose ^c				
ETVAX				

Placebo

^aMild or greater vomiting after first, second, or both doses on day 0.

^bn (percent of row total)

^cExclude full dose recipients (n=5) from analysis.

TABLE 14.3.1.7a:

Number and Percentage of Participants Experiencing Unsolicited Adverse Events with 95% Confidence Intervals by MedDRA® System Organ Class and Preferred Term, and Treatment Group - Adults

			Place (N=X		ET	VAX I	Full Dose XX)		AX Ful 0 μg dr (N=X			oined Va (N=XX)	
MedDRA® System Organ Class	MedDRA® Preferred Term	n	n % (95% CI)				(95% CI)	n	%	(95% CI)	n	%	(95% CI)
Any SOC	Any PT		n /0 (9370 C1)										
[SOC 1]	Any PT												
	[PT 1]												
	[PT 2]												
[SOC 2]	Any PT												
	[PT 1]												
	[PT 2]												

N= Number of participants in the Safety Population. A participant is only counted once per preferred term and system organ class.

TABLE 14.3.1.7b:

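### Apart from Day 0 vomiting in children, the SAP plans no direct estimate of the reactogenicity that dmLT adds at a fixed ETVAX dose

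*SAP*

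**What the plan says.** SAP 2.1 gives as one purpose: "This study provides an opportunity to test the safety profile of a mucosal adjuvant, double-mutant LT (dmLT), in adults and children". The primary objective (3.1.1) is the safety and tolerability of ETVAX given alone and "together with different dosages of dmLT adjuvant in descending age groups in Bangladesh".

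For solicited events, 9.1.1 applies Fisher's exact test to "compare the proportion of participants with solicited reactogenicity events between each of the vaccine arms with the placebo arms". It then forms three pools (vaccine without dmLT, vaccine with dmLT, all vaccine): "all vaccine arms will be combined and each will be compared to placebo". The footnote to the Table 14.3.1.5 shells agrees: "P-value is from a Fisher's exact test, testing the treatment vs placebo".

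The same section plans one model with an adjuvant term, a logistic regression of vomiting with "covariates for sex, age group (i.e., cohort's B, C and D), dose and adjuvant in the model". Its shell, Table 14.3.1.6.1, is limited to Day 0 and to vaccinated children aged 6 to 59 months, with rows for dmLT 0, 2.5, 5 and 10 µg. Table 14.3.1.6.2, for all children, has no dmLT row. Tables 14.3.1.1(a)-(d) give each arm's proportion with an exact 95% CI. Of the Fisher comparisons, 9.1.1 says "they are not considered formal statistical hypothesis tests".

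For immunogenicity, by contrast, Section 8 plans comparisons of vaccine with and without dmLT, and 3.1.2 makes the adjuvant effect on immune response a secondary objective.

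**The concern.** Because no arm receives dmLT alone (4.4.2), what it adds shows only when arms with and without it are compared at the same antigen dose. The design contains such arms in every part, but the solicited-event comparisons do not use them. Nor do the pools help in Parts B-D: Combined ETVAX Alone mixes antigen doses (in Part D 1/8, 1/4 and 1/2), while the dmLT pool sits at one dose.

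The risk is in the reading. A reader who finds the dmLT arm significant against placebo and the same-dose arm without dmLT not significant will conclude that dmLT causes the event. That is not a comparison of the two arms. Conversely, where both arms exceed placebo, a real dmLT increment has no estimate attached to it.

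**Working it through.** **Where a same-dose comparison exists (4.3, 4.4.2; planned sizes)**

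| Part | ETVAX alone | Same dose + dmLT | Same cohort? | Placebo |
|---|---|---|---|---|
| A | full, 15 | 10 µg, 15 | yes, A1, 1:1:1 | 15 |
| B | 1/2, 15 (B2) | 2.5, 5, 10 µg, 3×15 = 45 (B4-B6) | no | 6×10 = 60 |
| C | 1/2, 15 (C2) | 2.5, 5 µg, 2×15 = 30 (C3-C4) | no | 4×10 = 40 |
| D | 1/4, 30 (D2) | 2.5, 5 µg, 2×30 = 60 (D4-D5) | no | 5×10 = 50 |

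Actual sizes may differ: a footnote to Table 14.3.1.6.1 refers to 5 full-dose recipients.

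**The plan's own figures.** Section 5 gives none for a dmLT contrast. Its chances of seeing at least one event, 1 − (1 − p)^n, reproduce:
- n = 15: 80.4% at p = 10.3% and 90.1% at 14.3%.
- n = 30: 80.5% at 5.3% and 90.0% at 7.4%.
- Zero-event bounds, 1 − 0.05^(1/n): 18.1% and 9.5%.

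**Does the vomiting regression estimate a dmLT effect?** Excluding full dose, Parts B-D have 5 + 4 + 5 = 14 vaccine arms. Leaving sex aside, the model needs 1 + 2 (age) + 2 (dose) + 3 (dmLT) = 8 columns, and the design matrix has rank 8. So dmLT effects adjusted for ETVAX dose are estimable, assuming additivity on the logit scale. As laid out, the shell takes 10 µg as reference, so 0 v 10 µg is the only with/without odds ratio shown directly.

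**How often would two placebo tests disagree if dmLT did nothing?** Let π(b) be the chance that one vaccine arm is significant (two-sided Fisher, 5%) when placebo has b events. With two same-dose arms at the same true rate, the chance that exactly one is significant is Σ P(b)·2π(b)(1 − π(b)). In half of these cases it is the dmLT arm. The SAP gives no event rates, so these are assumptions; placebo is set at 5%.

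| Arm, arm, placebo | Vaccine rate | Exactly one significant |
|---|---|---|
| 15, 15, 60 (Part B) | 10% | 14% |
| | 20% | 41% |
| | 25% | 44% |
| | 30% | 38% |
| | 40% | 18% |
| 15, 15, 15 (Part A) | 10% | 1% |
| | 25% | 24% |
| 30, 30, 50 (Part D) | 25% | 33% |

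**What would same-dose contrasts deliver?** Power is for two-sided 5% Fisher tests of 10% v 25%, by full enumeration of both binomials. Approximate 95% half-width with both rates at 10%: 1.96·√[0.1·0.9·(1/n₁ + 1/n₂)].

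| Contrast | Power | Half-width (points) |
|---|---|---|
| 15 v 15 (A, or one level in B or C) | 9% | 21.5 |
| 15 v 30 (C pooled) | 14% | 18.6 |
| 15 v 45 (B pooled) | 14% | 17.5 |
| 30 v 60 (D pooled) | 35% | 13.1 |
| 75 v 150 (all parts, unstratified) | 77% | 8.3 |

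The last row sums 15 + 15 + 15 + 30 = 75 and 15 + 45 + 30 + 60 = 150. It ignores age strata and the sequential cohorts, so it is optimistic.

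**The case against.** The SAP presents the Fisher comparisons as a screen for events needing clinical evaluation, and placebo is a natural comparator for that. Where it wants dmLT set against vaccine alone it says so, and only for immune response. Both points stand, but a screen against placebo still cannot attribute a signal to adjuvant or antigen.

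Four stronger readings are tempting, and the document does not support them:
- That dmLT is never contrasted with vaccine alone for reactogenicity. The vomiting regression does this, within its limits.
- That the trial cannot say what dmLT adds. Arm-level proportions with exact CIs are tabulated for every solicited event, so same-dose arms can be set side by side. What is missing is a planned difference with its interval.
- That the increment is the trial's primary question. The primary objective covers safety with dmLT but names no contrast between arms.
- That the matched arms in Parts B-D isolate the dmLT effect. They sit in different cohorts recruited step-wise, each randomised only against its own placebo, so calendar time can confound the contrast.

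The discordance also depends on the assumptions: 44% is the highest case checked, and with adult sizes at low event rates it almost vanishes.

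**Conclusion.** The point holds as a gap in planned estimation. There is no direct same-dose dmLT estimate for elevated temperature, loose stools, diarrhea, abdominal pain, nausea, allergic reaction or any symptom in the age groups where each is collected. In adults there is none for any event, vomiting included, so the only concurrently randomised dmLT contrast in the trial is left out.

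The misreading it invites ranges from about 1% to 44% of trials in the cases checked, under assumed event rates, planned group sizes and an inert dmLT. The missing estimates would be imprecise (half-widths of about 13 to 22 points within parts at a 10% rate). That argues for reporting intervals rather than adding tests, and a wide interval should not be read as evidence that dmLT adds nothing.

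**What to change.** Keep the placebo comparisons. In 9.1.1 and Tables 14.3.1.5a-d, for each solicited event and for any symptom, add the risk difference with exact 95% CI between ETVAX + dmLT (each level, and levels pooled) and the same ETVAX dose alone. In detail:
- Name adults as the main randomised contrast.
- Label the Part B-D contrasts as non-randomised comparisons of sequential cohorts.
- Do not use the mixed-dose Combined ETVAX Alone pool as comparator.
- Stratify any summary across parts by age group.
- Present all of these as exploratory estimates, without significance claims.

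The cost is a paragraph of SAP text and a few rows per table; no new data or participants are needed. The downside is more unadjusted, imprecise exploratory comparisons, a limitation that 9.1.1 already acknowledges for its existing ones.

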4 INVESTIGATIONAL PLAN

4.1 Overall Study Design and Plan

This is a Phase I/II single site, double-blind, randomized, placebo-controlled, dose-escalation, age-descending study that will start testing the vaccine in healthy adults, and move sequentially into toddlers, younger children and infants. The study is designed to have 4 parts. All participants will receive two doses of vaccine with or without dmLT adjuvant on an outpatient basis. Before moving to the next lower age group, available safety data will be evaluated and reviewed by the icddr,b Data Safety Monitoring Board (DSMB), after which they will make a recommendation whether to proceed to the next age group.

The study will have 4 parts; Part A (Adult ages 18-45 years), Part B (Toddlers ages 24-59 months), Part C (Younger Children ages 12-23 months) and Part D (Infants ages 6-11 months). Each participant will receive two doses of either ETVAX with dmLT adjuvant, ETVAX without dmLT adjuvant or Placebo. Each participant will be assessed for reactogenicity for 7 days following dose 1 and dose 2. All participants will be followed for safety for six months after the last vaccination, with a scheduled home visit.

The unblinded study pharmacist or member of the IP formulation team will be aware of group allocation, although he/she will not be able to influence or decide this allocation nor be part of the safety assessment. This will ensure that the study team involved in assessment of safety outcomes, as well as participants, are unaware of the identity of the study vaccine administered. This will help rule out bias at the time of assessment. As the reference product and study vaccines are different in appearance and composition, the vaccinator blind will be maintained through the use of the unblinded study pharmacist or member of the IP formulation team who will prepare the vaccines.

In addition, immunogenicity assessments are planned to assess adjuvant effect of dmLT on vaccine immune responses compared to responses when giving vaccine alone in descending age-groups. The study will seek to establish the safety and optimal dose response of study vaccine within each age-group.

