4.3 Selection of Study Population

This will be a single site study conducted at the Mirpur field site by the icddr,b. The first part (Part A) will enroll a total of 45 adult participants (30 vaccinees and 15 placebos) into one Cohort. The second part (Part B) will enroll a total of 150 toddlers (24-29 months) into 6 separate cohorts to be recruited in step-wise

fashion. Each cohort will enroll 25 toddlers (15 vaccinees and 10 placebos). The third part (Part C) will enroll a total of 100 younger children (12-23 months) into 4 separate cohorts in a step-wise fashion. Each cohort will enroll 25 younger children (15 vaccinees and 10 placebos). The fourth part (Part D) will enroll a total of 200 infants (6-11 months) into 5 separate cohorts to be recruited in a step-wise fashion. Each cohort will enroll 40 infants (30 vaccinees and 10 placebos). Toddlers, younger children and infants will only be enrolled if their parents are fully informed about the study and provide consent for their child's participation.

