6.3.2 Safety Population

All participants in the enrolled population who receive a study vaccination and have safety data available will be included in the safety population. Treatment groups for safety analysis will be assigned according to the actual treatment received at the first vaccination. If a participant receives mixed doses (e.g., an ETVAX dose without dmLT at Dose 1 and the same ETVAX at Dose 2 with dmLT), the safety data collected after the start of the mixed dosing (e.g., post Dose 2) will be excluded from the analysis. All excluded data will be presented in the data listings. All safety analyses will be performed using this population.

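### The vomiting model's text reverses the Part-to-age mapping, and its ETVAX-versus-placebo table omits the five full-dose children without a stated reason

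*SAP*

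**What the plan says.** Section 9.1.1 plans a logistic regression of vomiting after any ETVAX dose, "with covariates for sex, age group (i.e., cohort's B, C and D), dose and adjuvant in the model". It then translates the letters into ages: "The age group categories will correspond with cohorts B, C and D: 6-11 months, 12-23 months, and 24-59 months, respectively". On who is analysed it says: "Results will be summarized for all vaccinated children in Table 14.3.1.6.1 and all children in Table 14.3.1.6.2". It states no exclusion.

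The design section assigns the ages the other way round: "Part B (Toddlers ages 24-59 months), Part C (Younger Children ages 12-23 months) and Part D (Infants ages 6-11 months". Sections 4.3.1.2 and 4.4.2 agree with the design section.

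The shells of Tables 14.3.1.6.1 and 14.3.1.6.2 list age in months, with 24 to 59 as the reference row and no cohort letter. Footnote c, attached to the dose variable in both, removes the full-dose recipients and gives their number as five. In Table 14.3.1.6.2 the dose variable has only two rows, ETVAX and placebo, and the title still reads "Among All Children 6 to 59 Months of Age".

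Section 6.3.2 says of the Safety population: "All safety analyses will be performed using this population". Section 9.1 repeats this and adds that every reported adverse event enters the summaries and analyses.

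**The concern.** There are two faults in the same analysis. The sentence defining the age covariate swaps Parts B and D. It is a definition, so a programmer who follows it puts toddlers in the infant row and infants in the reference row. And both tables leave out a group defined by the dose received, which contradicts the text that governs them and the Safety-population rule. Neither Section 9.1.1 nor Section 12, which records changes to planned analyses, mentions the omission.

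Safety and tolerability are the primary objective, and vomiting is the only solicited event given a regression across age, dose and adjuvant. An inverted age effect would mislead about the youngest children. An unexplained omission of vaccinees makes the ETVAX-versus-placebo result in children something other than what its title claims.

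**Working it through.** **Age mapping.** The two definitions side by side:

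| Part | Sections 4.1, 4.3.1.2, 4.4.2 | Section 9.1.1 model text |
|---|---|---|
| B | 24-59 months | 6-11 months |
| C | 12-23 months | 12-23 months |
| D | 6-11 months | 24-59 months |

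Coding by the right-hand column only relabels a categorical covariate. The fit and the sex, dose and adjuvant coefficients do not change, but the row called 6-11 months is then Part B and the reference row is Part D. The reported 6-11 versus 24-59 odds ratio is therefore one over the true one: 1/2.0 = 0.5.

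The SAP gives no vomiting rates. Assume 20% (6-11 months), 10% (12-23) and 5% (24-59), so the odds are 0.25, 0.111 and 0.0526.
- Correct coding: 0.25/0.0526 = 4.75 for 6-11 versus 24-59, and 0.111/0.0526 = 2.11 for 12-23 versus 24-59.
- Coding as written: 0.0526/0.25 = 0.21 and 0.111/0.25 = 0.44.

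**Exclusion: who is dropped.** Section 4.4.2 assigns the full dose, among children, only to toddler cohort B3, so by assignment the five are toddlers given ETVAX without dmLT. B3 was planned with 15 vaccinees. The figure of five is an observed count and cannot be derived from the plan. The SAP does not say whether the B3 placebo children stay in.

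**Exclusion: how much it matters.** Planned child vaccinees (Section 4.3) are 6×15 + 4×15 + 5×30 = 300. With B3 at five instead of 15 this is 290. Planned placebo children are 6×10 + 4×10 + 5×10 = 150, all assumed to remain. The five are 5/290 = 1.7% of vaccinees.

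Illustration with assumed counts: 28 of the other 285 vaccinees and 8 of 150 placebo children vomit.
- Five excluded: (28/257)/(8/142) = 1.93. The standard error of the log odds ratio is √(1/28 + 1/257 + 1/8 + 1/142) = 0.414, giving a Wald 95% interval of about 0.86 to 4.36.
- Five included, with k of them vomiting: ((28+k)/(262−k))/(8/142), which is 1.90 for k = 0, 2.12 for k = 3 and 2.28 for k = 5.

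The largest change is 2.28/1.93 = 1.18, or 18%. Over a wider assumed grid (placebo 2-10%, other vaccinees 5-30%, 0 to 5 of the five vomiting), the odds ratio with the exclusion is 0.74 to 1.025 times the one without it.

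**The case against.** On age, the shells are what programmers build from. They label the rows in months, age in months is a defined variable (Section 3.3, item 10), and every Part D table is titled as infants. Inversion needs someone to label Part D children as 24 to 59 months against their recorded ages. That stands as a reason to think the error would probably be caught. It does not make the sentence right.

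On the exclusion, a reader might infer that the full-dose children's vomiting is hidden. It is not. The footnotes disclose the count, and full dose has its own column in Tables 14.3.1.1(b), 14.3.1.2(b) and 14.3.1.5b, the last with a Fisher test against placebo. Table 14.3.1.3(b) gives it by day and Listing 16.2.7.1b by child. Those comparisons are within Part B, however. Table 14.3.1.6.2 is the one that pools ETVAX against placebo over all three child age groups.

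A reader might also infer that the five were dropped because they vomited, so that the vaccine effect is biased downwards. The SAP does not support this. It says that the 1/2 dose was the one chosen to go forward in toddlers, but not why, and it does not mention vomiting as the reason.

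In Table 14.3.1.6.1, which estimates dose levels, a level of five children, all in one age group and all without dmLT, is hardly estimable. Leaving it out there is defensible. Finally, Section 9.1.1 describes these comparisons as screening and not as formal tests, and the SAP attaches no cohort-progression decision to this model. That limits the stakes.

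**Conclusion.** Both inconsistencies are in the text and should be corrected before the tables are programmed. The age sentence is wrong as written. Its consequence, a reciprocal 6-11 versus 24-59 month odds ratio, follows only if age is coded from the cohort letter.

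The exclusion contradicts Section 9.1.1 and the Safety-population rule in both tables. In Table 14.3.1.6.2 it has no evident justification, because dose is collapsed to ETVAX versus placebo and five more vaccinees create no sparsity. Because it is defined by the dose received, it is not a random omission and could shift the odds ratio. On the assumed counts the shift is from 1.93 to somewhere between 1.90 and 2.28, well inside the sampling interval. Its direction depends on vomiting data the document does not contain. The figures rest on planned cohort sizes, five B3 vaccinees, all planned placebo children retained, and assumed vomiting rates.

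**What to change.** - In Section 9.1.1, correct the sentence to Part B = 24-59 months, Part C = 12-23 months and Part D = 6-11 months, or define the covariate by age in months at enrollment.
- Delete footnote c from Table 14.3.1.6.2 so that all vaccinated children are included and the title is true.
- In Table 14.3.1.6.1 the exclusion may stay. State it and its reason in Section 9.1.1 and in the table title, and show the full-dose counts (vomited, did not vomit) in a row without an odds ratio.

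The cost is a corrected sentence, a deleted footnote, an added sentence and title qualifier, and one extra row of counts. No additional Firth or exact model is needed.
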